### **7.1.10 EurQol EQ-5D-5L Health Questionnaire**

EQ-5D-5L is a standardised measure of health status developed to provide a simple, generic measure of health for clinical and economic appraisal. The EQ-5D-5L consists of a descriptive system and an EQ Visual Analogue scale (EQ VAS) and EQ-5D-5L is designed for self-completion by respondents. The questionnaire is cognitively undemanding and taking only a few minutes to complete. EQ-5D-5L will be completed by the participating subjects at Days 8, 15, 29, 57, 92, 180, and 360.

## **7.2 Safety Assessments Related to Endpoints**

### **7.2.1 Adverse Events**

AEs will be recorded during the study period, from obtaining the informed consent until end-of-study visit 10. For further information on definitions and reporting of AEs and SAEs, see [Section 9](#).

### **7.2.2 Safety Local Laboratory**

Blood samples for safety laboratory evaluations of clinical chemistry and haematology parameters will be collected during study as described below. Actual sampling time will be recorded. Clinically significant abnormal findings will be reported as AEs. Findings at the

screening visit will be recorded in the medical history section in the eCRF. Clinical chemistry and haematology will be analysed locally.

Urine samples for safety evaluations will be taken as described below. Samples will be measured with dipstick and analysed locally. In case of abnormal results, a microscopic test will be measured.

The investigator will review the laboratory results and evaluate and document whether the results are normal or abnormal and whether abnormal results are non-clinically or clinically significant.

The following parameters will be collected:

- Clinical chemistry:
  - P-alanine aminotransferase (ALT), P-gamma glutamyl transferase, P-alkaline phosphate, P-bilirubin total, P-creatinine, P-potassium, P-albumin, P-calcium, P-immunoglobulin G (IgG)
- Haematology:
  - B-haemoglobin, B-haematocrit, B-white blood cell count, B-neutrophils (absolute count), B-lymphocytes (absolute count), B-eosinophiles (absolute count), B-platelet count
- Urinalysis(dipstick):
  - U-glucose, U-haemoglobin, U-protein, U-pH

Time of collection:

- All the above analyses:
  - At screening within 7 days prior to inclusion
  - Day 1: Prior to imlifidase administration
  - Days 2, 3 (prior to IVIg infusion), 8, 15 and 29

### 7.2.3 Physical Examination

A complete physical examination will be performed at screening and Day 180 (visit 9) and include an assessment of the following: general appearance, head and neck, lymph nodes, abdomen, musculo-skeletal, cardiovascular, respiratory and gross neurological examination. The physical examination shall be performed by an investigator.

### 7.2.4 Vital Signs

Blood pressure, pulse rate, respiratory frequency, oxygen saturation and body temperature will be assessed at:

- Screening

- Day 1:
  - Predose
  - 1 and 2 hours after end of imlifidase dosing
- Days 8, 15, and 29 (all except body temperature)

At Day 1 the subject will be observed for 2 hours after end of imlifidase infusion, longer if medically indicated. If the subject is without infusion related symptoms and vital signs are normal the observation period ends 2 hours after end of infusion.

Systolic and diastolic blood pressure will be measured after the subject has been in supine position for at least 5 minutes. All recordings will be performed using validated standard equipment. Clinically significant abnormal findings will be reported as AEs.

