### Background and Scientific Justification for Conducting the Study

Guillain-Barré Syndrome is an acute, paralyzing, inflammatory disease of the peripheral nervous system usually preceded by an infection or other immune stimulation that induces an aberrant autoimmune response targeting peripheral nerves and their spinal roots. It is the most frequent cause of acute neuromuscular weakness in the Western world and can occur at any age. GBS is a rapidly progressive disorder often leading to a severe paralysis of the arms and legs. Most GBS patients have sensory disturbance (tingling or numbness or ataxia) and pain, and some patients have double vision or problems with swallowing. GBS may also paralyse the respiratory muscles, leading to intensive care unit admission and mechanical ventilation. The cause of GBS is believed to be anti-nerve autoantibody induction by infections that frequently precede the onset of disease.

After onset, GBS patients have highly varying prognoses. Despite modern care, the mortality rate is 3-5%. Two thirds of the patients have severe symptoms resulting in their inability to walk unaided, and 20-30% require mechanical ventilation for a period ranging from weeks to months. Progression of weakness in GBS is usually rapid and reaches a nadir within 4 weeks in the majority of patients, but many develop their maximum deficit within 2 weeks. Even with subsequent recovery from the acute condition, many patients suffer from long-term complications, leaving 20% unable to walk after 6 months.

To treat GBS, both general medical care and immunological treatment are recommended. Supportive care, including monitoring of respiratory function by frequent measurement of vital capacity and other clinical outcomes, is needed to prevent or to manage complications. Intravenous Immunoglobulin (IVIg) and Plasma Exchange (PE) are the two main treatment options aimed at attenuating the autoreactive humoral immune response. A review performed in

2014 showed that IVIg and PE were equally effective in treating GBS and the frequency of adverse events was similar with either treatment. Unlike many other neurological conditions with an autoimmune basis, patients with GBS do not respond to corticosteroids.

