### **7.1.8 Mechanical Ventilation**

Number of days on mechanical ventilation from screening up until Day 180 will be collected.

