### 3.3 Safety analysis set

All treated subjects are included in the safety analysis set (SAF).

The safety analysis set will be used for presentation of safety endpoints.

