#### 4.8.2.2 Vital signs

Vital signs will be presented by visit (i.e., time point) for each parameter and summarised, including absolute change from baseline. Shift tables will be presented from baseline to all planned time points until end of residual drug effect, i.e. Day 29. Any changes from normal/low to high or from normal/high to low during these periods will be counted as a shift and will be summarised. The results will be flagged as Low (L)/High (H) as per the criteria defined in [Appendix 3](#).

In addition, separate listings containing vital signs data will be presented by subject.

The vital signs assessment part of visit 3, 7 and 9 has only been collected up to protocol version 7.0 (inclusive). Results from these visits will only be presented in the listing.

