### 9.3 Appendix 3 - Vital Sign Parameters Normal Ranges

All vital signs measurement results below/above the normal range will be flagged as Low (L)/High (H) results, as per criteria defined below:

Vital Sign Parameter	Lower range	Upper range
Systolic Blood Pressure (mmHg)	less than 120	140 or higher
Diastolic Blood Pressure (mmHg)	less than 80	90 or higher
Oxygen Saturation (%)	less than 95	NA
Pulse Rate (beats/min)	less than 60	100 or higher
Respiratory Rate (breaths/min)	less than 12	20 or higher
Body Temperature (C)	less than 36.4	37.8 or higher

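### Respiratory frequency and oxygen saturation tables pool ventilated with unsupported readings, so these two safety summaries can mislead in either direction

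*Protocol*

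**What the plan says.** Protocol 7.2.4 schedules the readings: "Blood pressure, pulse rate, respiratory frequency, oxygen saturation and body temperature will be assessed at" screening, Day 1 (predose, then 1 and 2 hours after the infusion ends) and, except for temperature, Days 8, 15 and 29. SAP 4.8.2.2 sets the summary: "Vital signs will be presented by visit (i.e., time point) for each parameter and summarised, including absolute change from baseline". Shift tables run from baseline to Day 29, and the counting rule is: "Any changes from normal/low to high or from normal/high to low during these periods will be counted as a shift and will be summarised". Protocol 12.3.3.1 has the same counting rule.

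The categories come from SAP Appendix 3: "All vital signs measurement results below/above the normal range will be flagged as Low (L)/High (H) results". Respiratory rate is Low below 12 and High at 20 or more. Oxygen saturation is Low below 95 and has no upper limit. The population is the safety set, which is every treated subject (SAP 3.3).

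Ventilation is handled elsewhere. Protocol 7.1.8 states: "Number of days on mechanical ventilation from screening up until Day 180 will be collected". SAP 4.7.4 derives ventilator days from start and end dates, tabulates GBS DS 5 by time point, and plans a count of subjects in an ICU or on a ventilator at dosing. No section links these data to the vital signs tables.

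**The concern.** Mechanical ventilation supports both breathing rate and oxygenation. A reading taken on a ventilator therefore describes the subject plus the support, and an in-range value does not mean what it means in a subject breathing unaided. The documents do not state this premise; it is simply what such support is for.

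The situation is foreseeable. The Protocol synopsis says of GBS patients that "20-30% require mechanical ventilation for a period ranging from weeks to months". Entry requires GBS DS of at least 3 with no upper limit, and spells lasting weeks would span some or all of the Day 8, 15 and 29 readings.

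At stake is whether a reader of the two safety tables can tell a recovered reading from a supported one. As planned, the reader cannot. These are also the only scheduled numeric respiratory measures in the study: vital capacity is mentioned in the Protocol background but is not in the flow chart.

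**Working it through.** The plan states no figure on this point, so there is none to reproduce. The check applies the SAP's own rules to illustrative readings, which are not trial data.

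**1. How many subjects could be involved.** Inputs: about 30 subjects (SAP 2.2) and 20-30% ventilated (Protocol synopsis; SAP 1).
- Expected number ever ventilated: 30 × 0.20 = 6 to 30 × 0.30 = 9.
- Binomial probability of at least 3 among 30: 0.956 at 20% and 0.998 at 30%.
- The 20-30% refers to all GBS patients, whereas the trial enrols those unable to walk unaided, given as two thirds of patients. If every ventilated patient comes from that group (an assumption), the share is 0.20/(2/3) = 30% to 0.30/(2/3) = 45%, or 9 to 13.5 of 30.

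All of these count subjects ever ventilated. The documents give no figure for the number on a ventilator at a particular visit.

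**2. What the rules do to a reading.** Only Normal or Low to High, and Normal or High to Low, count as shifts.

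| Parameter | Baseline | Later reading | Category | Change | Counted? |
|---|---|---|---|---|---|
| Rate | 18 | 14, ventilated | Normal to Normal | -4 | no |
| Rate | 18 | 34, unsupported | Normal to High | +16 | yes |
| SpO2 | 96 | 98, ventilated | Normal to Normal | +2 | no |
| SpO2 | 96 | 86, unsupported | Normal to Low | -10 | yes |
| Rate | 24 | 14, ventilated | High to Normal | -10 | no |
| Rate | 24 | 34, unsupported | High to High | +10 | no |
| SpO2 | 93 | 98, ventilated | Low to Normal | +5 | no |
| SpO2 | 93 | 86, unsupported | Low to Low | -7 | no |
| Rate | 14, ventilated | 24, weaned | Normal to High | +10 | yes |
| SpO2 | 98, ventilated | 93, weaned | Normal to Low | -5 | yes |

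Three patterns follow.
- From a normal baseline, ventilation removes a shift that would have been counted without support.
- From a baseline already High on rate or Low on saturation, the count is the same either way, but the change from baseline reverses sign.
- From a ventilated baseline, weaning adds a counted shift.

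**3. Effect on a mean.** Assume 6 to 9 of 30 subjects are ventilated at one visit with a saturation change of +5, and the rest change by -1.
- With 6: (6 × 5 - 24 × 1)/30 = 6/30 = +0.2.
- With 9: (9 × 5 - 21 × 1)/30 = 24/30 = +0.8.
- Non-ventilated readings alone: -1.0.

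The pooled mean has the opposite sign. This places every ever-ventilated subject at the same visit, so it is a demanding case.

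**4. Effect on a shift rate.** Assume 2 non-ventilated subjects shift adversely and the 6 to 9 ventilated subjects read in range.
- Pooled: 2/30 = 6.7%.
- Non-ventilated denominator: 2/24 = 8.3% to 2/21 = 9.5%.
- Counting every ventilated subject as adverse: 8/30 = 26.7% to 11/30 = 36.7%.

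Changing the denominator matters little here. How the ventilated subjects are classed matters a great deal.

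**The case against.** The strongest reply is that respiratory failure is well covered elsewhere. GBS DS 5 is tabulated by time point and appears in the GBS DS shift tables (SAP 4.7.1, 4.7.4). Ventilator and ICU days are summarised and listed. Adverse events are tabulated on all treated subjects, and SAP 4.7.3 anticipates respiratory failure coded as an event. GBS DS is scored at Days 8, 15 and 29, the same visits as the later vital signs. The study is descriptive, and no stated decision depends on these shift counts. All of this stands, and it limits the importance of the point. It does not repair the two tables: the DS 5 and ventilator-day outputs are efficacy outputs on the full analysis set, and nothing ties them to individual readings in the safety-set tables.

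A second reply is that pooling is inferred from silence. SAP 4.1.1 lets the output shells specify otherwise, and the shells are not in the documents. That is fair. If the shells already separate ventilated readings, the text needs only to say so.

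A reader might go further and infer that the plan records the worst respiratory outcome as normal, or that the shift counts are always biased towards reassurance. The documents support neither. The outcome is captured by the other routes above, and weaning can add adverse shifts. Nor is a Low-to-Normal saturation change credited as a shift; any apparent improvement comes from the change summary and an uncounted table cell.

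**Conclusion.** The point holds as a limited reporting defect. For respiratory frequency and oxygen saturation only, SAP 4.8.2.2 and Appendix 3 mix supported and unsupported readings with nothing to distinguish them, and the resulting means and shift counts can err in either direction.

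The size is unknown. Six to 9 of 30 ever ventilated rests on the general 20-30% applying to this trial. The higher range rests on the further assumption about the non-walking group. A reader might want to turn these into a number of affected readings per visit, but that needs the share ventilated on a given day, which the documents do not give. Subjects ventilated at dosing are provided for in the SAP, but there may be none. The worked readings show the mechanism, not its frequency.

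The change is worth making because it is specific and cheap. The account of respiratory outcome in the trial as a whole does not depend on it.

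**What to change.** In SAP 4.8.2.2:
- Derive an on-ventilator flag for each respiratory-rate and oxygen-saturation reading, including baseline, from the ventilation start and end dates and the same-visit GBS DS.
- In the shift tables for these two parameters, show an unranked category for readings on mechanical ventilation, with its count.
- Present values and changes from baseline separately for ventilated and non-ventilated readings, alongside the planned all-subject summary.
- State that readings on the day ventilation starts or stops are classified by date only, because the SAP 4.7.4 formulas use dates without times.

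Two simpler remedies are less suitable. Dropping ventilated readings would take the sickest subjects out of the tables. Ranking ventilation below Low would merge a separately reported disease outcome into a vital sign and, as the last calculation shows, would dominate the result.

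The cost is one derived flag from existing data, a few extra rows and small cell counts. The flag does not address supplemental oxygen, for which no status is recorded with the reading. The SAP change log shows version 2.0 was finalised during the main analysis, so if the tables already exist, the split can be added in the clinical study report or its Day 360 addendum and documented as a change to the plan.

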### 7.2.5 ECG

No ECGs will be collected.

## 7.3 Other Assessments

### 7.3.1 Demographics and Baseline data

Information about gender, race and age at inclusion, weight and height will be collected at the screening visit for each subject. Measurements should be taken without shoes and overcoat.

### 7.3.2 Baseline GBS Disease Information

The following information will be collected when first available:

- GBS variant (pure motor GBS, pharyngeal-cervical-brachial weakness, Miller Fisher syndrome [no limb weakness], Miller Fisher-GBS overlap syndrome, pure sensory GBS, ataxic form, other)
- Cranial nerve involvement
- Electrophysiology classification of subtypes (acute motor axonal neuropathy [AMAN], acute inflammatory demyelinating neuropathy [AIDP], unresponsive nerves, responsive nerves but not classifiable [equivocal], normal).

### 7.3.3 Serology

Determination of HIV-1 and HIV-2 antibodies, hepatitis B surface-antigen and hepatitis C virus antibodies will be performed at screening.

### 7.3.4 Pregnancy Test

Serum  $\beta$ -hCG will be determined for all female subjects at screening and on Day 180 (visit 9), using validated standard methods.

### **7.3.5 Medical History**

Information regarding medical history will be collected at the screening visit for each subject and recorded in the eCRF. Medical history will include information regarding any comorbidities affecting mobility and/or respiration.

### **7.3.6 Nerve Conduction Study (NCS)**

If assessed, nerve conduction study (NCS) will be measured at Days 15 and 29. NCS is performed using standard techniques at least on one side of the body. The skin temperature should be controlled and maintained between 32 °C and 34 °C. The NCS includes median, ulnar, peroneal, and tibial motor responses and superficial radial, and sural sensory responses. The median nerve is stimulated at the wrist, antecubital fossa, and responses are recorded over the abductor pollicis brevis. The ulnar nerve is stimulated at the wrist, below the elbow, and responses are recorded over the abductor digiti minimi. The peroneal nerve is stimulated at the ankle, fibular head, and responses are recorded over the extensor digitorum brevis. The tibial nerve is stimulated at the ankle and popliteal fossa, and responses are recorded over the abductor hallucis. Measurements include distal latency, negative peak duration, baseline-to-peak amplitude, conduction velocity, and minimum F-wave latencies. To define conduction block (CB), we used the consensus criteria of the American Association of Electrodiagnostic Medicine (Olney et al. 2003).

### **7.3.7 SARS-CoV-2 virus PCR-test**

At the screening visit an evaluation of the result of the SARS-CoV-2 virus PCR-test, performed at hospital admission or later, will be done.

## 8. BIOLOGICAL SAMPLING PROCEDURES

### 8.1 Handling, Storage and Destruction of Biological Samples

Safety samples will be disposed after analyses according to local laboratory practice.

PK, PD, ADA and biomarker samples may be stored for at maximum of 5 years after completion of the study report.

Details on handling of biological samples are described in the laboratory manual that will be provided to the site prior to inclusion of the first subject.

### 8.2 Chain of Custody of Biological Samples

A full chain of custody is maintained for all samples throughout their life cycle.

The principal investigator keeps full traceability of collected biological samples from the subjects while in storage at the centre until shipment and keeps documentation of receipt of arrival.

The sample receiver keeps full traceability of the samples while in storage and during use until used or disposed.

Hansa Biopharma keeps oversight of the entire life cycle through internal procedures, monitoring of study sites and auditing of external laboratory providers.

### 8.3 Withdrawal of Informed Consent for Biological Samples

If a subject withdraws consent to the use of biological samples, the samples will be disposed/destroyed, if not already analysed and documented.

The principal investigator:

- Will ensure that subject withdrawal of informed consent is notified immediately to Hansa Biopharma.
- Will ensure that biological samples from that subject, if stored at the study site, are immediately identified, disposed/destructed and the action documented.
- Will ensure the local laboratory(ies) holding the samples is/are informed about the withdrawn consent immediately and that samples are disposed/destructed, and the action documented returned to the study site.

Hansa Biopharma ensures the central laboratory(ies) holding the samples is/are informed about the withdrawn consent immediately and that samples are disposed/destructed, and the action documented returned to the study site.

In the event that analysis/research has already been performed, Hansa Biopharma will retain the results and associated data for regulatory reasons, but these will not be used in any subsequent analyses.

## 9. ADVERSE EVENTS AND SERIOUS ADVERSE EVENTS

### 9.1 Definitions

#### 9.1.1 Adverse Event

An AE is the development of an undesirable medical condition or the deterioration of a pre-existing medical condition following or during exposure to a pharmaceutical product, whether or not considered causally related to the product. Relationship to the study drug will be deemed as not related, unlikely, possible or probable. An undesirable medical condition can be symptoms (e.g., nausea and chest pain), signs (e.g., tachycardia and enlarged liver) or the abnormal results of an investigation (e.g., laboratory findings and electrocardiograms).

In cases of surgical or diagnostic procedures, the condition/illness leading to such a procedure is considered as the AE rather than the procedure itself.

In case of a fatality, the cause of death is considered as the AE, and the death is considered as its outcome.

#### 9.1.2 Serious Adverse Event

An SAE is an AE or suspected adverse reaction that is considered "serious" if, in the view of either the investigator or Hansa Biopharma, it results in any of the following outcomes:

- Results in death
- Is immediately life-threatening
- Requires in-patient hospitalisation or prolongation of existing hospitalisation
- Results in persistent or significant disability or incapacity
- Is a congenital abnormality or birth defect
- Is an important medical event that may jeopardise the subject or may require medical intervention to prevent one of the outcomes listed above. Examples of such events include allergic bronchospasm requiring intensive treatment in an emergency room or at home, or convulsions that do not result in inpatient hospitalization, or the development of drug dependency or drug abuse.

**Life-threatening event:** An adverse event or suspected adverse reaction is considered "life-threatening" if, in the view of either the investigator or Hansa Biopharma, its occurrence places the patient or subject at immediate risk of death. It does not include an adverse event or suspected adverse reaction that, had it occurred in a more severe form, might have caused death.

**Disability** is defined as a substantial disruption in a person's ability to conduct normal life functions.

**Hospitalisation:** Admittance to an emergency room for observation without being admitted to the hospital may be considered to be an AE but is not considered as an SAE. However, complications that occur during hospitalization are AEs, and if a complication prolongs hospitalisation, the event is considered serious.

The death of a subject is *per se* not an event but an outcome, but the cause of the death is.

